Analysis of AEs of interest showed that dissociative side effects, sedation and amnesia (investigator reported) were seen at both the 0.16 mg/kg and 0.32 mg/kg MIJ821 doses. Amnesia in particular was dose dependent and more common at the higher MIJ821 dose (42.1% with MIJ821 0.32 mg/kg vs 9.5% with MIJ821 0.16 mg/kg pooled doses). No AEs of amnesia was seen in Ketamine or Placebo arms. About one-quarter of patients in each active treatment group experienced dissociative side effects (23.8% for 0.16 mg/kg pooled dose and 26.3% in 0.32 pooled mg/kg dose), versus 50% with Ketamine and 10% with placebo. Sedation was seen at both active doses (14.3% at the lower pooled dose and 21.1% at 0.32 mg/kg pooled dose vs 10% with ketamine and 0% with placebo).

Time to onset of dissociative side effects, amnesia and sedation was short, occurring within the 40 minutes of infusion in most cases for both MIJ821 doses and for placebo, though somewhat longer than with ketamine. Median time to onset for adverse event of sedation was shorter for the lower MIJ821 dose (pooled 0.16 mg/kg dose, 0.25 hours) than the higher dose (pooled 0.32 mg/kg dose, 1.46 hours), versus 0.10 hours for ketamine and no cases (0.0 hours) for placebo.

Most events of amnesia resolved within 4 hours (median time to resolution was 3.27 hours). Median time to resolution for dissociation ranged from 5.25 hours for MIJ821 0.16 mg/kg

pooled dose versus 3.72 hours for MIJ821 0.32 mg/kg pooled dose, and shorter times for ketamine (1.02 hours) and placebo (2 hours). Events of sedation resolved faster for the pooled 0.16 mg/kg dose than 0.32 mg/kg pooled dose (median time 1.6 hours vs 2.5 hours). Ketamine time to resolution was 0.47 hours.

At both MIJ821 investigated doses, increases in mean supine systolic and diastolic blood pressure were observed at the first sampling time of 1 hour after start of the 40 min infusion. The placebo-adjusted mean change from baseline in supine SBP and DBP appeared to peak between 2 to 4 hours after start of infusion ( $< 20$  mmHg) with a clear trend of recovery to baseline within 4 hours (DBP) and 6 hours (SBP) after start of infusion.

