## 8 Visit schedule and assessments

The Assessment Schedule ([Table 8-1](#)) lists all of the assessments as well as when they are performed. All data obtained from these assessments must be supported in the participant's source documentation and recorded in the clinical database, received electronically or in source only, as indicated.

Participants should be seen for all visits/assessments as outlined in the assessment schedule ([Table 8-1](#)) or as close to the designated day/time as possible ( $\pm 3$  days visit window is allowed). Missed or rescheduled visits should not lead to automatic discontinuation.

In case a visit is performed outside the schedule, subsequent visits shall be performed in accordance to the original visit schedule. In addition to the scheduled visits, patients may have unscheduled visits at the discretion of the Investigator. Data collected during unscheduled visits will be recorded in the unscheduled visit CRFs. Participants who prematurely discontinue the study for any reason should be scheduled for a visit as soon as possible, at which time all of the assessments listed for the final visit will be performed. At this final visit, all adverse events and concomitant medications should be recorded on the CRFs.

Please see [Appendix 6](#) for the scales recall periods.

[figure not shown]
If the COVID-19 pandemic limits or prevents on-site study visits, alternative methods of providing continuing care may be implemented by Novartis. Phone calls, virtual contacts (e.g. teleconsult) or visits by site staff/home nursing service to the participant's home depending on local regulations and capabilities, can replace on-site study visits, for the duration of the pandemic until it is safe for the participant to visit the site again. The collection of samples may also be modified by the Sponsor and will be communicated to the Investigator.

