2.1.2 Analysis period and visit remapping

All study data of participants will be grouped into Core Period and Extension Period according to [Table 2-1](#). For those who take retreatment for relapse, assessments during retreatment will be grouped into Retreatment Period specially.

Table 2-1 Analysis Period for Data

Analysis Period	Start Time Point	End Time Point
Core Period	Day 1	For participant who won't join in Extension Period: Date of End of study visit; For participant who join in Extension Period: End of Core visit (Day 43)
Extension Period	For participant who join in Extension Period: Date of End of Core visit + 1	For participant who join in Extension Period: Date of End of Study visit
Retreatment Period	For participant who take retreatment: Date of first dose of retreatment	For participant who take retreatment: Date of last Retreatment visit

Analysis visit and windows

Since the actual visit for a participant may not exactly coincide with their targeted visit date, the actual visit date will be mapped to an analysis visit for the purpose of data summary and model analysis. However for assessments (except for PK sampling) performed at -2 hours, -1 hour, 20 min, 40 min, 2 hours, 4 hours on the same day, there is no need to remap visit time, so site collected timepoint will be analysed.

The visit window in [Table 2-2](#) defines the analysis visit applicable for assessments in Core Period and Extension Period, including efficacy endpoints (e.g. MADRS, [REDACTED]), safety endpoints (e.g. laboratory, vital signs, ECG, [REDACTED]).

Table 2-2 Analysis Visit Windows for Core Period and Extension Period

Analysis Period	Study Visit	Target Day/Time	Study Day
Core Period	Baseline	Day 1 -2 hours predose (See definition for baseline in Section 2.1.1)	-2, - 1, 1 (predose)
	D1 20 min, 40 min, 2 h, 4 h	Day 1 20 min, 40 min, 2 hours, 4 hours post dose	1 (post dose)
	24 h	2	2
	D8	8	3 - 11
	D15 -2 h, -1 h, 40 min, 2 h, 4 h	Day 15 -2 hours, -1 hour predose, 40 min, 2 hours, 4 hours post dose	12 - 18
	D22	22	19 - 25
	D29 -2 h, -1 h, 40 min, 2 h, 4 h	Day 29 -2 hours, -1 hour predose, 40 min, 2 hours, 4 hours post dose	26 - 32
	D36	36	33 - 39
	D43	43	40 – End of Core Visit
Extension Period	2 weeks follow-up	57	(End of Core Visit + 1) - 64
	4 weeks follow-up	71	65 - 85
	Monthly follow-up post Day 43	43 + (n)*28 n is the nth month follow up	(-13, +14) of target day The last follow-up visit will last until the end of study

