The main analyses will summarize data collected in Core Period up to 2 weeks follow up in Extension Period. The monthly follow-up visit in Extension Period will not be presented in by-visit summary, unless otherwise specified.

In addition for participants who are retreated during Extension Period, assessments performed during Retreatment Period will be mapped to the analysis visit according to [Table 2-3](#).

Table 2-3 Analysis Visit Windows for Retreatment Period

Analysis Period	Study visit	Target Day since start of retreatment*	Day since start of retreatment*
Retreatment Period	Baseline of Retreatment	Day 1 -2 hours pre-retreatment (See definition for	1

		baseline of retreatment in Section 2.1.1)	
	Retreatment D1 40 min, 2 h, 4 h	Day 1 40 min, 2 hours, 4 hours post retreatment	1
	Retreatment 24 h	2	2
	Retreatment D8	8	3 - 11
	Retreatment D15 -2 h, -1 h, 40 min, 2 h, 4 h	Day 15 -2 hours, -1 hour predose, 40 min, 2 hours, 4 hours post dose	12 - 18
	Retreatment D22	22	19 - 25
	Retreatment D29 -2 h, -1 h, 40 min, 2 h, 4 h	Day 29 -2 hours, -1 hour predose, 40 min, 2 hours, 4 hours post dose	26 - 32
	Retreatment D36	36	33 - 39
	Retreatment D43	43	40 – End of Retreatment Visit

* See the definition for Day(s) since start of retreatment in [Section 2.1.1](#)

When multiple assessments are mapped into the same window, following rules will be applied for efficacy and safety endpoints (except ECG) and PROs:

When assessments for scheduled visit and unscheduled visit are both present within the same window, the scheduled assessments value should be used. Unscheduled visit will only be used when there is no measurement from the scheduled visit in the defined window. Two special cases need to be handled as following rule:

- When assessments on a dosing day drop to the window of a non-dosing visit, for example the dosing on Day 15 was delayed to the window of Day 22, the pre-dose assessment will be mapped to the non-dosing visit of Day 22, while the post-dose assessment will not be mapped. Unless scheduled assessments for Day 22 were performed, the scheduled ones should be mapped then.
- When assessments on non-dosing day drop to the window of a dosing visit, for example the visit Day 8 was delayed to Day 15 and no dosing was administered, assessments will be mapped to the pre-dose hour of this dosing visit. Unless the dosing were administered and scheduled assessments performed within the window, the scheduled assessments should be mapped then.

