In case of multiple assessment values among the same type of visit (i.e. two unscheduled assessments) within the same analysis window, the closest to the scheduled visit day will be used. In case of equal distances (e.g same day), the latest assessment value will be used. The exception is an assessment at early study withdrawal visits along with another assessment within a window. In such cases, the early-withdrawal assessment will be used.

For ECG, the same strategy will be applied except that no prioritization of scheduled vs unscheduled visit will be made.

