2.6.4.2 Vital signs

[figure not shown]
The change from baseline of vital signs (systolic/diastolic blood pressure, pulse rate, temperature) and weight will be summarized by treatment arm and by analysis visit, for Core Period up to 2 weeks' follow up visit, and separately for the Retreatment Period.

[figure not shown]
In addition, for systolic/diastolic blood pressure, the change from most recent dose will be summarized in a similar manner.

For Core Period up to 2 weeks follow up visit, the mean (SD) of change from baseline will be displayed by line plot. The change from the each dose up to 2 weeks will be plot in the same manner.

The proportion of any clinical relevant abnormality postbaseline and break donw by visit will be summarized and presented in listing at individual level.

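### Post-dose blood pressure, pulse and ECG readings drop out of the by-visit safety summaries when the second or third infusion falls in a non-dosing visit window

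*SAP*

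**What the plan says.** SAP Table 2-2 defines the Core windows by study day: D8 = 3-11, D15 = 12-18, D22 = 19-25, D29 = 26-32, D36 = 33-39, D43 = 40 to the End of Core visit. After Day 1, only D15 and D29 have post-dose slots. The windows cover "safety endpoints (e.g. laboratory, vital signs, ECG" among other data.

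Where several assessments fall in one window, the "following rules will be applied for efficacy and safety endpoints (except ECG) and PROs". One special case begins "When assessments on a dosing day drop to the window of a non-dosing visit". The example is a Day 15 infusion delayed into the Day 22 window, and the instruction is that "the pre-dose assessment will be mapped to the non-dosing visit of Day 22, while the post-dose assessment will not be mapped". A later sentence brings ECG in: "For ECG, the same strategy will be applied except that no prioritization of scheduled vs unscheduled visit will be made".

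SAP 2.6.4.2 summarizes vital signs by arm and analysis visit and adds that "for systolic/diastolic blood pressure, the change from most recent dose will be summarized in a similar manner". SAP 2.6.4.1 summarizes ECG values, and their change from the most recent dose, for each visit, and gives the incidence of abnormal ECGs by arm and analysis visit and in a listing.

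Protocol Section 8 allows ±3 days per visit and states: "Missed or rescheduled visits should not lead to automatic discontinuation".

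**The concern.** A 2 h blood pressure reading is informative because it was taken 2 h after an infusion. Whether that infusion was given on Day 18 or Day 19 hardly changes its meaning, yet under the SAP the first enters the by-visit tables and the second does not.

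The early hours matter. In the proof-of-concept study the placebo-adjusted blood pressure change "appeared to peak between 2 to 4 hours after start of infusion" (Protocol 4.5). The affected infusions are the second and third, which are the ones that separate repeated from single dosing, and the safety profile by dose and regimen feeds the choice of the Phase 3 dose (SAP 2.11). The SAP amendment added the change-from-most-recent-dose summaries for ECG and blood pressure; the mapping rule removes from them readings that were taken as planned relative to the infusion.

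**Working it through.** The documents give no figure to reproduce. The check passes each possible infusion day through the Table 2-2 windows and the special-case rule.

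**Protocol window against SAP window.** 15 ± 3 = Days 12-18 and 29 ± 3 = Days 26-32. These equal the D15 and D29 windows, so an infusion within the protocol's tolerance always keeps its post-dose readings.

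**Outcome by infusion day.**

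| Infusion | Study day given | Window | Post-dose readings |
|---|---|---|---|
| Second | 8-11 | D8 | not mapped |
| Second | 12-18 | D15 | mapped |
| Second | 19-25 | D22 | not mapped |
| Second | 26-32 | D29 | mapped, as D29 |
| Second | 33 onward | D36 or D43 | not mapped |
| Third | 19-25 | D22 | not mapped |
| Third | 26-32 | D29 | mapped |
| Third | 33 onward | D36 or D43 | not mapped |

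The first late day is 15 + 4 = 19 for the second infusion and 29 + 4 = 33 for the third. The first infusion cannot be affected, because SAP 2.1.1 defines Day 1 as the first dose date. Table 2-3 repeats the same windows for the Retreatment Period.

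**Readings lost per affected infusion** (Protocol Table 8-1): blood pressure 3 time points, pulse 3, ECG 2. That is 3 + 3 + 2 = 8 time points, and in triplicate 8 × 3 = 24 readings.

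**Number of infusions.** With 195 randomized, 195 × 2 = 390 second and third infusions are planned. At these two infusions the placebo arm and both single-infusion arms receive placebo: (30 + 30 + 30) × 2 = 180. The other four arms receive MIJ821: (15 + 30 + 30 + 30) × 2 = 210. So 180/390 = 46% are placebo.

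**Illustration.** The rate of infusions given outside the window is an assumption.

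| Assumed rate | Of 390 | Of 210 active | Per infusion, arm of 30 | Chance of at least one in an arm of 30, 1 − (1 − p)^30 |
|---|---|---|---|---|
| 2% | 7.8 | 4.2 | 0.6 | 0.455 |
| 5% | 19.5 | 10.5 | 1.5 | 0.785 |
| 10% | 39 | 21 | 3.0 | 0.958 |

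In the 0.0048 mg/kg arm of 15, the expected number per infusion is 0.3, 0.75 and 1.5. The last column treats participants as independent. The counts also include any infusion that falls in another dosing window and so stays mapped, which makes them slightly high.

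**The case against.** **The wording may mean only that the reading is not mapped to Day 22.** SAP 2.1.2 also says that same-day time points need no remapping and are analysed as the site recorded them. That sentence keeps the hour label (2 h, say) but assigns no visit. No other visible rule gives the reading a visit, so on either reading it has no row in a by-visit table. The clause that prefers scheduled Day 22 assessments only replaces the mapped pre-dose value.

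**A reader might infer that every post-dose reading after an off-schedule infusion is lost.** The documents do not support that. A second infusion on Days 26-32 is mapped, though as D29, and the first infusion, which carries the primary endpoint and the Holter recording, is never touched.

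**A reader might also infer that the safety data disappear or the signal is hidden.** They need not. Individual listings, treatment-emergent adverse events, adverse events of special interest (which include blood pressure changes and QT prolongation) and the proportion with any post-baseline vital-sign abnormality do not have to depend on mapping. PK concentrations use windows of elapsed time from each infusion. Whether the plot of change from each dose depends on mapping is not specified.

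**Bias is a third tempting inference.** Visits delayed for intoxication are to stay within the permitted window (Protocol 6.2.1.1), so they remain mapped. The blood pressure rule in Protocol 10.2.3 withholds the next infusion and looks to the next scheduled visit, which describes a skipped dose and not a late one. Other routes remain possible, such as waiting for an electrolyte or liver value before resuming, but nothing shows that they are common or differ by arm.

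**Numbering infusions 1, 2, 3 would create a new error.** This stands. SAP 2.2.1 allows the Day 15 infusion to be skipped, and the Day 29 infusion would then be labelled the second. Moving the 4 h MADRS by infusion is also debatable, because the supportive MADRS model is built on study time.

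**Conclusion.** The point holds in a limited form. Followed as written, SAP 2.1.2 removes valid post-infusion blood pressure, pulse and ECG readings from the by-visit safety tables for second and third infusions that fall in a non-dosing window. ECG is somewhat more exposed than vital signs: its abnormality incidence is planned by visit and in listings, with no overall post-baseline proportion stated.

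The size depends on how often infusions fall outside the protocol's window, which the documents do not say. At an assumed 2-10% the loss is 0.6-3 participants per 30-person arm at each infusion, and a little under half of the affected infusions would be placebo if lateness is unrelated to arm. The established consequence is less complete and less precise descriptive tables. A link between delay and risk, and hence bias, is possible but not shown. The primary analysis is not affected.

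**What to change.** In SAP 2.1.2, for post-dose vital signs and ECG, replace the non-mapping rule by assignment to (a) the scheduled dosing visit to which the infusion belongs, Day 15 or Day 29 as recorded, and (b) nominal time from the start of that infusion, whatever the study day. Using the recorded visit and not an ordinal count keeps a Day 29 infusion labelled Day 29 when Day 15 was skipped. State that change from the most recent dose uses that infusion's own pre-dose reading, even where that reading is mapped to another visit. Keep the study-day windows for pre-dose, non-dosing and MADRS assessments, and apply the same rule to Table 2-3.

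The cost is SAP wording and programming; no new data are needed. The one drawback is that a few readings in a dosing-visit row will come from a different study day than the others. A footnote giving their number per arm deals with that.

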2.1.3 Analysis sets

The Randomized Set (RAS) consists of all randomized participants. The descriptions of population will be based on RAS.

The Full Analysis Set (FAS) comprises all randomized participants who received at least one dose of randomized study treatment. Participants will be analyzed according to the treatment they have been assigned to during the randomization procedure. The primary efficacy analysis for data in Core Period will utilize this analysis set.

The Safety Set (SAF) includes all participants who received at least one dose of study treatment. Participants will be analyzed according to the treatment received. In case participants take the wrong treatment (different with the assigned treatment), the first treatment received will be used in analysis. Safety analysis for data in Core Period will be based on SAF.

The Extension Set (ENS) is defined to include all subjects who joined Extension Period. Data collected during follow-up period will be analyzed based on ENS, and grouped by the assigned treatment in Core Period. In case participants take the wrong treatment during Core, the first actual treatment taken will be used for the analysis of safety data only. The analysis of data collected during extension period (before and after re-treatment period) will be based on ENS.

The Retreatment Set (RTS) is defined as a subset of SAF including participants who received at least one dose for the retreatment of relapse. Participants will be analyzed according to the treatment received for the first injection during the Retreatment Period. The efficacy and safety endpoints pertinent to Retreatment Period (see [Table 2-1](#)) will be analyzed based on RTS.

PK Analysis Set (PKS) includes all participants who provided at least one evaluable PK concentration. Determined PK concentrations may be excluded from the PKS (per the scientific judgement of the PK scientist, e.g. non-plausible concentrations). All subjects within the PK analysis set will be included in the PK data analysis. PK samples from subjects treated with MJJ821 will be measured and PK samples from placebo treated subjects will not be measured.

[REDACTED]

[REDACTED]

[REDACTED]

[REDACTED]

[REDACTED]

[REDACTED]

[REDACTED]

[illegible]

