### 3.2 Double-blind Core Period

The double-blind Core Period starts on Day 1 and lasts 6 weeks. All baseline assessments (including the primary efficacy scale MADRS) must be performed on Day 1, prior to randomization. Investigational drug will be administered in a double-blind manner in the form

of a 40-minute intravenous infusion on Day 1, Day 15 and Day 29. Designated unblinded qualified site personnel is required for the preparation of the infusion prior to administration.

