### **12.1 Analysis sets**

The Full Analysis Set (FAS) comprises all randomized participants who received at least one dose of randomized treatment. Participants will be analyzed according to the treatment they have been assigned to during the randomization procedure.

The Safety Set includes all participants who received at least one dose of study treatment. Participants will be analyzed according to the study treatment received, where treatment received is defined as the randomized/assigned treatment if the participant took at least one dose of that treatment or the first actual treatment received if the randomized/assigned treatment was never received due to dispensing error.

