2.6.1 Adverse events (AEs)

Treatment-Emergent Adverse Events (TEAEs) are defined as adverse events starting or worsening after the first dose of study medication and up to 2 weeks post the last dose. For relapsed participants who receive retreatment of MIJ821 in Extension Period, adverse events starting after 2 weeks post the last dose of Core Period up to the start of retreatment will not be counted as TEAEs. The missing onset date of AE will be imputed before identify the TEAE (see imputation rule in [Appendix 5.1.1](#))

The Medical Dictionary for Regulatory Activities (MedDRA) version 24.0 or later will be used to code Adverse Event (AE) to a SOC and a PT.

TEAEs will be analyzed separately for Core Period and Retreatment Period:

- The summary of TEAEs in Core Period (up to 2 weeks post the last dose) will be based on SAF
- The summary of TEAEs in Retreatment Period (up to 2 weeks post the last dose of retreatment) will be based on RTS

The number (and percentage) of participants with TEAEs will be summarized by following approach as defined in [Table 2-7](#), in terms of all TEAEs, Treatment-Emergent Serious Adverse Events (TESAEs), TEAEs leading to treatment discontinuation, treatment-related TEAEs or TESAEs and death:

- by treatment, primary system organ class and preferred term
- by treatment, primary system organ class, preferred term and maximum severity
- by treatment, Standardized MedDRA Query (SMQ) and preferred term
- by treatment, preferred term with most frequent (incidence rate $\geq 5\%$)

Table 2-7 AE Summaries of Subject Incidence

Category	by SOC and PT	by SOC, PT and maximum severity	by most frequent PT (≥ 5%)
All TEAEs	Y	Y	Y
TESAEs	Y		
AEs leading to treatment discontinuation	Y		
Treatment-related TEAEs	Y		
Treatment-related SAEs	Y		
Deaths	Y		

For all AEs tables presented by SOC and PT (and grade), the SOC's will be presented in alphabetical order and PTs will be ordered within the SOC by decreasing order of frequency. AE tables by preferred term only will be sorted in descending order of frequency.

A participant with multiple adverse events within a primary system organ class is only counted once towards the total of the primary system organ class.

All AEs, deaths, SAEs and AEs leading to permanent study drug discontinuation will be listed separately.

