2.11 Interim analysis

One unblinded analysis will be performed when all participants completed Day 57 (2 weeks follow-up visit after the End of Core visit on Day 43). Data from Core Period will be analyzed according to the plan herein. The optimal dose will be identified based on the dose-response relationship established by MCP-Mod, as well the sustained efficacy effect, safety profile and PK of each MIJ821 dose and regimen compared to placebo.

This unblinded interim analysis will be conducted by study team. The individual level data will maintain blinded to investigators and participants until final database lock.

3 Sample size calculation

With the randomization ratio of 2:1:2:2:2 for the biweekly dosing arms, the sample size of 27:14:27:27:27 for placebo, MIJ821 0.0048 mg/kg, MIJ821 0.016 mg/kg, 0.048 mg/kg and 0.16 mg/kg, will provide about 80% power to detect a dose-response signal [to reject the null hypothesis of a flat dose-response curve where all MIJ821 dose means are equal to the placebo mean] for the biweekly dosing arms in change from baseline in MADRS at 24 hour using MCP-Mod methodology at the one-sided $\alpha = 0.05$ level. Since MIJ821 0.0048 mg/kg is

potentially non-effective, the sample size for this arm is chosen to be 50% of other arms and is sufficient for establishing the dose-response curve.

The 6 candidates DR curves (2 Emax, 4 Sigmoid Emax) for power calculation are defined in [Section 2.4.2.](#) [REDACTED]

[REDACTED]

For the two single infusion arms of 0.048 mg/kg and 0.16 mg/kg, to maintain the same precision as for the biweekly dosing arm vs placebo, 27 participants per arm are needed. In total the study needs 177 patients. Assuming a 10% dropout rate, approximately 195 pts in total (15 pts for 0.0048 mg/kg and 30 pts for the remaining 6 treatment arms) will be randomized.

All treatment arms (including both regimen) will be included in the MCP-Mod for the primary analysis which will provide about 92% power to detect a dose-response signal in change from baseline in MADRS at 24 hour using MCP-Mod at the one-sided 0.05 level.

4 Change to protocol specified analyses

Not applicable.

5 Appendix

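### SAP 2.1.3 and protocol 12.1 give different Safety Set rules for a wrongly treated participant, the difference is undeclared, and neither rule keeps post-MIJ821 events out of the placebo column

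*SAP*

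**What the plan says.** Protocol 12.1 analyses the Safety Set by treatment received and defines that term in two steps. First, "treatment received is defined as the randomized/assigned treatment if the participant took at least one dose of that treatment". Only failing that does it use "the first actual treatment received if the randomized/assigned treatment was never received due to dispensing error".

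SAP 2.1.3 also analyses by treatment received but without the first step: "In case participants take the wrong treatment (different with the assigned treatment), the first treatment received will be used in analysis". It repeats the idea for the Extension Set: "In case participants take the wrong treatment during Core, the first actual treatment taken will be used for the analysis of safety data only".

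The SAP section headed "4 Change to protocol specified analyses" contains only the statement that it does not apply.

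The rule feeds the main safety tables. SAP 2.6.1 states: "The summary of TEAEs in Core Period (up to 2 weeks post the last dose) will be based on SAF". The Core summaries of adverse events of special interest (SAP 2.6.1.1) fall under the same analysis set through SAP 2.6.

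**The concern.** Two programmers, one following each document, could produce different safety tables, and nothing in the SAP tells the reader that the rule changed.

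The SAP rule also gives an answer that is hard to defend. A participant assigned to 0.16 mg/kg every other week who receives saline in error on Day 1 and MIJ821 on Days 15 and 29 is analysed as placebo for the whole Core Period. Events after two correct MIJ821 infusions then sit in the column that serves as reference for every adverse event of special interest.

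The arms are small: 30 planned participants each, 15 at 0.0048 mg/kg. Safety is one of the inputs to the choice of Phase 3 dose and regimen (protocol 4.4, SAP 2.11). A single attribution can therefore be visible in a table.

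**Working it through.** **Inputs**
- Protocol rule (12.1): the assigned treatment if it was received at least once; otherwise the first treatment received.
- SAP rule (2.1.3): the first treatment received if any infusion was wrong; otherwise the assigned treatment.
- Core dosing (protocol 3.2): study drug is given in the form "of a 40-minute intravenous infusion on Day 1, Day 15 and Day 29", so a wrong first infusion can be followed by a correct one.
- Planned arm sizes (protocol 12.8.1, SAP Section 3): 30 on placebo.
- Proof-of-concept rates (protocol 4.5): amnesia 9.5% at pooled 0.16 mg/kg and no cases on placebo; sedation 14.3% and 0%.

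The documents state no figure to reproduce, so the check is an enumeration.

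**Step 1: both rules applied to every pattern.** A = MIJ821, P = placebo, in the order Day 1, 15, 29. This simplifies to one repeated-dose active treatment against placebo. The single-infusion arms, where later saline is scheduled, are taken up in step 3. Two assignments times eight infusion patterns give 16 cases.

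| Assigned | Given | Protocol | SAP | MIJ821 infusions tabulated as placebo (protocol / SAP) |
|---|---|---|---|---|
| A | AAA, AAP, APA, APP | A | A | 0 / 0 |
| A | PAA | A | P | 0 / 2 |
| A | PAP, PPA | A | P | 0 / 1 |
| A | PPP | P | P | 0 / 0 |
| P | AAA | A | A | 0 / 0 |
| P | AAP, APA | P | A | 2 / 0 |
| P | APP | P | A | 1 / 0 |
| P | PAA | P | P | 2 / 2 |
| P | PAP, PPA | P | P | 1 / 1 |
| P | PPP | P | P | 0 / 0 |

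**Step 2: counts.**
- The rules disagree in 3 + 3 = 6 of 16 cases, each with a wrong first infusion and a correct later one.
- The SAP rule puts MIJ821 exposure under placebo in 6 cases: PAA, PAP, PPA for participants assigned to A, and the same three for those assigned to P.
- The protocol rule also does so in 6 cases, all assigned to P: AAP, APA, APP, PAA, PAP, PPA.

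The patterns are not equally likely. The counts show what each rule permits, not how often it would happen.

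**Step 3: is the SAP label well defined?** At 0.048 and at 0.16 mg/kg, the biweekly and single-infusion arms have the same Day 1 infusion (protocol 6.1.3). A placebo participant given 0.16 mg/kg on Day 1 has a first treatment that fits two arms. A single-infusion participant given MIJ821 in error on Day 15 has the same problem under the SAP; under the protocol that participant stays in the assigned arm.

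**Step 4: size.**
- One affected participant who has the event adds about 1/30 = 3.3 percentage points to placebo incidence. Where the participant is moved into the placebo column from an active arm, the denominator becomes 31 and the figure is 1/31 = 3.2 points.
- Against an assumed 9.5-point amnesia difference, 3.3/9.5 = 35%.
- Both figures condition on the event occurring. If the participant has it with probability 0.095, the expected shift is 0.095 × 3.3 = 0.3 points; for sedation it is 0.143 × 3.3 = 0.5 points.

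**Step 5: the protocol rule plus one sentence.** Suppose nobody who received MIJ821 in Core is tabulated as placebo. The six cases left under the protocol rule all move to an active arm, leaving 0 of 16.

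**The case against.** The best reply is that the discrepancy does not itself create the contamination. Each rule permits it in six patterns, and for a placebo participant given MIJ821 first the SAP rule is the better one. That stands. A reader might infer that the SAP departure is what puts active-drug events under placebo, or that it systematically hides harm. The enumeration does not support either inference, and restoring the protocol wording alone would not cure the fault.

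A reader might also take the one-third-of-the-amnesia-difference figure as the likely effect. It is a worst case. It requires that the misallocated participant has the event, and the 9.5% is a pooled weekly and biweekly rate in treatment-resistant depression, not an expectation stated for this trial. Both amnesia and sedation had no placebo cases in that study; dissociation had 10% on placebo, so a single case would stand out less.

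The trigger is narrow. Unblinded site staff obtain the allocation through the IRT, which returns no kit for placebo participants (protocol 6.3.2, 6.7), and the documents give no dispensing-error rate. Much of the trail is already captured: treatment errors go on the dosing CRF (protocol Table 10-1), dose changes with reasons are listed (SAP 2.3.1), all adverse events are listed (SAP 2.6.1), and dosing-day events of special interest are listed with time from the first and the most recent dosing (SAP 2.6.1.1). These listings reduce the harm. They do not settle which column the participant enters in the summary tables.

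**Conclusion.** The conflict is real, undeclared and limited in reach. Followed as written, the SAP can tabulate events after two correct MIJ821 infusions as placebo events. That is a wrong rule rather than a missing detail. The protocol rule has the mirror fault, and the SAP wording does not always identify one of the seven arms.

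Few participants are likely to be affected, although without an error rate this is a judgement. The shift is about 3.3 points in placebo incidence for one affected participant who has the event, and about 0.3 to 0.5 points in expectation at the proof-of-concept amnesia and sedation rates. The planned adverse event summaries are descriptive, so no test depends on this. Primary efficacy is unaffected because the Full Analysis Set is analysed as randomised. The point should be corrected before unblinding, but it does not threaten the trial's main conclusion.

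**What to change.** Change the SAP only:

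1. In 2.1.3, align safety attribution for both the Safety Set and the Extension Set with protocol 12.1: assigned treatment if it was ever received.
2. Add that a participant who received any MIJ821 in Core is not tabulated as placebo.
3. State which arm applies when the biweekly and single-infusion regimens share the dose received.
4. List the events of every misallocated participant by the last treatment infused before onset.
5. Record in Section 4 any departure from protocol 12.1. Item 2 is one.

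The cost is a few sentences, one rarely used derivation and one listing, with no new data. Declaring the departure in the SAP means protocol 12.1 need not be rewritten, which under protocol 14.1 would need a formal amendment.

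There is a real downside. A placebo participant given MIJ821 only at a late infusion would have earlier saline-period events tabulated under an active arm. A single-infusion participant given MIJ821 in error on Day 15 would still be tabulated in the assigned arm. No single label per participant avoids this; the listing in item 4 makes it visible. The change concerns table attribution only and says nothing about dosing or patient management.
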